4.1.7 Organ Function Requirements

4.1.7.1 Adequate Bone Marrow Function Defined as:

- a. For patients with solid tumors without known bone marrow involvement:
 - Peripheral absolute neutrophil count (ANC) $\geq 1000/\text{mm}^3$
 - Platelet count $\geq 100,000/\text{mm}^3$ (transfusion independent, defined as not receiving platelet transfusions for at least 7 days prior to enrollment)
- b. Patients with known bone marrow metastatic disease will be eligible for study provided they meet the blood counts in Section

[4.1.7.1.a](#) (may receive transfusions provided they are not known to be refractory to red cell or platelet transfusions). These patients will not be evaluable for hematologic toxicity.

4.1.7.2 Adequate Renal Function Defined as:

- Creatinine clearance or radioisotope GFR $\geq 70\text{ml/min}/1.73\text{ m}^2$ or
- A serum creatinine based on age/gender as follows:

Age	Maximum Serum Creatinine (mg/dL)	
	Male	Female
1 to < 2 years	0.6	0.6
2 to < 6 years	0.8	0.8
6 to < 10 years	1	1
10 to < 13 years	1.2	1.2
13 to < 16 years	1.5	1.4
≥ 16 years	1.7	1.4

The threshold creatinine values in this Table were derived from the Schwartz formula for estimating GFR (Schwartz et al. J. Peds, 106:522, 1985) utilizing child length and stature data published by the CDC.

4.1.7.3 Adequate Liver Function Defined as:

- Bilirubin (sum of conjugated + unconjugated) $\leq 1.5 \times$ upper limit of normal (ULN) for age
- SGPT (ALT) ≤ 135 U/L. (For the purpose of this study, the ULN for SGPT is 45 U/L.)
- Serum albumin ≥ 2 g/dL.

4.1.7.4 Adequate Cardiac Function Defined As:

- Shortening fraction of $\geq 27\%$ by echocardiogram, or
- Ejection fraction of $\geq 50\%$ by gated radionuclide study.
- QTc interval ≤ 480 milliseconds

4.1.8 Patients must be able to swallow intact capsules.

4.1.9 Informed Consent: All patients and/or their parents or legally authorized representatives must sign a written informed consent. Assent, when appropriate, will be obtained according to institutional guidelines.

4.2 Exclusion Criteria

4.2.1 Pregnancy or Breast-Feeding

Pregnant or breast-feeding women will not be entered on this study due to risks of fetal and teratogenic adverse events as seen in animal/human studies. Pregnancy tests must be obtained in girls who are post-menarchal. Males or females of reproductive potential may not participate unless they have agreed to use an effective contraceptive method for the duration of study treatment and for 3 months after last dose of BVD-523FB (ulixertinib).

4.2.2 Concomitant Medications

4.2.2.1 Corticosteroids:

Patients receiving corticosteroids who have not been on a stable or decreasing dose of corticosteroid for at least 7 days prior to enrollment are not eligible. If used to modify **immune adverse events** related to prior therapy, \geq 14 days must have elapsed since last dose of corticosteroid (See [Section 4.1.6.1.d](#)).

4.2.2.2 Investigational Drugs:

Patients who are currently receiving another investigational drug are not eligible.

4.2.2.3 Anti-cancer Agents:

Patients who are currently receiving other anti-cancer agents are not eligible.

4.2.2.4 Anti-GVHD agents post-transplant:

Patients who are receiving cyclosporine, tacrolimus or other agents to prevent graft-versus-host disease post bone marrow transplant are not eligible for this trial.

4.2.2.5 CYP3A4 Agents:

Patients who are currently receiving drugs that are strong inducers or inhibitors of CYP3A4 are not eligible. Strong inducers or inhibitors of CYP3A4 should be avoided from 14 days prior to enrollment to the end of the study. See [Appendix II](#) for a list of agents. Note: CYP3A4 inducing anti-epileptic drugs and dexamethasone for CNS tumors or metastases, on a stable dose, are allowed.

4.2.2.6 CYP2D6 and CYP1A2: Patients who are currently receiving drugs that are strong inducers or inhibitors of CYP1A2 and CYP2D6 are not eligible. Strong inhibitors of CYP1A2 (eg., ciprofloxacin, enoxacin, fluvoxamine, zafirlukast) should be avoided from 14 days prior to enrollment to the end of the study. Strong inhibitors of CYP2D6 (e.g., bupropion, paroxetine, fluoxetine, quinidine, terbinafine) should also be avoided from 14 days prior to enrollment to the end of the study.

4.2.2.7 Patients with known significant ophthalmologic conditions (uncontrolled glaucoma, history of retinal vein occlusion or retinal detachment, excluding patients with longstanding findings secondary to existing conditions) are not eligible.

4.2.3 Infection: Patients who have an uncontrolled infection are not eligible.

4.2.4 Patients who have received a prior solid organ transplantation are not eligible.

4.2.5 Patients who in the opinion of the investigator may not be able to comply with the safety monitoring requirements of the study are not eligible.

5.0 TREATMENT PROGRAM

5.1 Overview of Treatment Plan

Treatment Schedule Table	
Days 1-28	BVD-523FB (ulixertinib) orally twice daily
Day 28	Evaluation

Patients will receive BVD-523FB (ulixertinib) twice daily, continuously for 28-day cycles (please see dosing nomogram in [Appendix V](#)). Evaluations will occur at the end of every other cycle x 3, then every 3 cycles. A cycle may be repeated up to a total duration of therapy of 2 years (maximum 26 cycles).

Drug doses should be adjusted based on the BSA calculated from height and weight measured within 7 days prior to the beginning of each cycle. Take by mouth on an empty stomach either 1 hour before a meal or 2 hours after a meal. Capsules should not be opened, crushed or chewed. If a patient misses or vomits a dose of BVD-523FB (ulixertinib), an additional dose should not be taken. Patients should resume dosing at the next scheduled time.

Therapy will be discontinued if there is evidence of progressive disease or drug related dose-limiting toxicity that requires removal from therapy ([Section 6.0](#)). Therapy may otherwise continue for up to 2 years provided the patient meets the criteria for starting subsequent cycles ([Section 5.2](#)) and does not meet any of the criteria for removal from protocol therapy criteria ([Section 10.0](#)).

5.1.1 Determination of Recommended Phase 2 Dose (RP2D)/Tolerable Dose

Dose Level	BVD-523FB (ulixertinib)Dose (mg/m ²)
-1	175 mg/m ² /dose PO BID* (300 mg BID Max Dose)
1*	260 mg/m²/dose PO BID* (450 mg BID Max Dose)
2	350 mg/m ² /dose PO BID* (600 mg BID Max Dose)

*Refer to the dosing nomogram in [Appendix V](#) for more information.

The starting BVD-523FB (ulixertinib) dose will be 260 mg/m²/dose (Dose Level 1), which is approximately 25% below the adult MTD. Accrual will be temporarily suspended after enrollment to the first 6 toxicity-evaluable subjects to assess for toxicity as outlined in [Section 11](#).

If there are fewer than 2 DLTs in the first 6 toxicity-evaluable subjects enrolled at the starting dose, the dose will be escalated to Dose Level 2. If ≥ 2 of the first 6 toxicity-evaluable subjects enrolled at Dose Level 2 have DLTs, all subsequent subjects will be enrolled at the original starting dose. Otherwise, remaining subjects will continue to enroll at Dose Level 2.

If there are 2 or more DLTs during cycle 1 among the first 6 toxicity-evaluable subjects enrolled at Dose Level 1, the next cohort will enroll at Dose Level -1. If ≥ 2 of the first 6 toxicity-evaluable subjects enrolled at the reduced dose have

DLTs, the study will be closed for toxicity. Otherwise, remaining subjects will continue to enroll at Dose Level -1.

5.1.2 Therapy Delivery Map

See [Appendix VI](#) for therapy delivery map for Cycle 1 and subsequent cycles.

5.1.3 Intra-Patient Escalation

Intrapatient dose escalation is not allowed.

5.2 **Criteria for Starting Subsequent Cycles**

A cycle may be repeated every 28 days if the patient has at least stable disease and has again met laboratory parameters as defined in the eligibility section, [Section 4.0](#) and eligible to continue agent administration per the requirements in [Section 6.0](#)

5.3 **Grading of Adverse Events**

Adverse events (toxicities) will be graded according to the current version of the NCI Common Terminology Criteria for Adverse Events (CTCAE). All appropriate treatment areas should have access to a copy of the current version of the CTCAEv5.0. A copy of the CTCAEv5.0 can be downloaded from the CTEP website (<http://ctep.cancer.gov>). Any suspected or confirmed dose-limiting toxicity should be reported immediately (within 24 hours) to the Study Chair.

5.4 **Definition of Dose-Limiting Toxicity (DLT)**

DLT will be defined as any of the following events that are possibly, probably or definitely attributable to protocol therapy. Dose limiting hematological and non-hematological toxicities are defined differently. The DLT evaluation period for the purpose of dose escalation will be Cycle 1 of therapy.

5.4.1 Non-Hematological Dose-Limiting Toxicity

5.4.1.1 Any Grade 3 or greater non-hematological toxicity attributable to the investigational drug with the specific exclusion of:

- Grade 3 nausea and vomiting of less < 3 days duration
- Grade 3 liver enzyme elevation, including ALT/AST/GGT that returns to levels that meet initial eligibility criteria or baseline within 7 days. See [Appendix XI](#) for values that represent thresholds between CTCAE grades.

Note: For the purposes of this study the ULN for ALT is defined as 45 U/L regardless of baseline.

- Grade 3 or 4 fever < 5 days duration.
- Grade 3 infection < 5 days duration.
- Grade 3 hypophosphatemia, hypokalemia, hypocalcemia or hypomagnesemia responsive to supplementation.

- Any Grade 2 visual disturbance that persists for ≥ 1 week.
- Any Grade 2 non-hematological toxicity that persists for ≥ 7 days and is considered sufficiently medically significant or sufficiently intolerable by patients that it requires treatment interruption.
- Note: Allergic reactions that necessitate discontinuation of study drug will not be considered a dose-limiting toxicity.

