6.2 Dose Modifications for Non-Hematological Toxicity

- 6.2.1 If a patient experiences non-hematological dose-limiting toxicity as defined in [Section 5.4.1](#), the treatment will be held. When the toxicity resolves to meet eligibility parameters or baseline within 14 days of drug discontinuation, the patient may resume treatment at a reduced dose (see [Appendix V](#) for capsule formulation dosing nomogram). Doses reduced for toxicity will not be re-escalated, even if there is minimal or no toxicity with the reduced dose.
- 6.2.2 If toxicity does not resolve to meet eligibility or baseline parameters within 14 days of drug discontinuation, the patient must be removed from protocol therapy.
- 6.2.3 If dose-limiting toxicity recurs in a patient who has resumed treatment at the

reduced dose, the patient must be removed from protocol therapy.

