Grade 2	
IV hydration as needed
 
Drugs that are strong inhibitors or inducers of CYP1A2, CYP2D6, and CYP3A4 must be avoided (see Sections 4.2.2.5 and 4.2.2.6; Appendix II).
	
 • Medical management • Continue BVD-523FB (ulixertinib). • If Grade 2 nausea persists for \geq 7 days and is considered sufficiently medically significant or sufficiently intolerable by patients that it requires treatment interruption per Section 5.4.1.1 will be considered a DLT. Hold BVD-523FB (ulixertinib) until nausea resolves to baseline and restart with one dose level reduction per Section 6.2.
Grade 3		
 • Medical management. • Hold BVD-523FB (ulixertinib). • If Grade 3 nausea persists for > 3 days, this will be considered a DLT. Hold BVD-523FB (ulixertinib) until nausea resolves to baseline and restart with one dose level reduction per Section 6.2.

If treatment is delayed by > 14 days or a DLT recurs after dose reduction, permanently discontinue BVD-523FB (ulixertinib).

Management and Dose Modification Guidelines for Vomiting

Vomiting	Adverse Event Management	Dose modification
Grade 1	5-HT3 antagonist and additional anti-emetics as needed	
 • Medical management. • Continue BVD-523FB (ulixertinib).

Grade 2	IV hydration as needed Drugs that are strong inhibitors or inducers of CYP1A2, CYP2D6, and CYP3A4 must be avoided (see Sections 4.2.2.5 and 4.2.2.6; Appendix II).	
• Medical management• Hold BVD-523FB (ulixertinib).• If Grade 2 vomiting resolves in < 7 days, may resume BVD-523FB (ulixertinib) once vomiting resolves to Grade ≤1.• If Grade 2 vomiting persists for ≥ 7 days, this will be considered a DLT. Hold BVD-523FB (ulixertinib) until vomiting resolves to baseline and restart with one dose level reduction per Section 6.2.
Grade 3		
• Medical management.• Hold BVD-523FB (ulixertinib).• If Grade 3 vomiting persists for > 3 days, this will be considered a DLT. Hold BVD-523FB (ulixertinib) until vomiting resolves to baseline and restart with one dose level reduction per Section 6.2.
Grade 4		Off protocol therapy

If treatment is delayed by > 14 days or a DLT recurs after dose reduction, permanently discontinue BVD-523FB (ulixertinib).

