13.4 Definition of Onset and Resolution of Adverse Events

Note: These guidelines below are for reporting adverse events on the COG case report forms and do not alter the guidelines for CTEP-AERS reporting.

- 13.4.1 If an adverse event occurs more than once in a course (cycle) of therapy only the most severe grade of the event should be reported.
- 13.4.2 If an adverse event progresses through several grades during one course of therapy, only the most severe grade should be reported.
- 13.4.3 The duration of the AE is defined as the duration of the highest (most severe) grade of the Adverse Effects.
- 13.4.4 The resolution date of the AE is defined as the date at which the AE returns to baseline or less than or equal to Grade 1, whichever level is higher (note that the resolution date may therefore be different from the date at which the grade of the AE decreased from its highest grade). If the AE does not return to baseline the resolution date should be recorded as "ongoing."
- 13.4.5 An adverse event that persists from one course to another should only be reported once unless the grade becomes more severe in a subsequent course. An adverse event which resolves and then recurs during a different course, must be reported each course it recurs.

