APPENDIX IV CORRELATIVE STUDIES

Correlative Study	Section.	Blood Volume		Tube Type
		Volume per Sample	Total Cycle 1	
Pharmacokinetics	8.4	2 mL	24 mL	K ₂ EDTA lavender top
Total Blood Volume in Cycle 1			24 mL	

Correlative Study	Section	Blood Volume		Tube Type
		Volume per Sample	Total Cycle 5 Day 1	
Circulating tumor DNA (optional)	8.5	
 For patients \geq 10 kg collect 20 mLs (10 mL per tube x 2 tubes) For patients \geq 5 kg but $<$ 10 kg collect 10 mL (one tube) For patients $<$ 5 kg research samples will not be collected 	10-20 mL	Streck Cell-Free DNA BCT tubes
Total Blood Volume in Cycle 5 Day 1			10-20 mL	

Correlative Study	Section	Blood Volume		Tube Type
		Volume per Sample	Total 'Time of progression' or 'End of protocol therapy'*	
Circulating tumor DNA (optional)	8.5	
 For patients \geq 10 kg collect 20 mLs (10 mL per tube x 2 tubes) For patients \geq 5 kg but $<$ 10 kg collect 10 mL (one tube) For patients $<$ 5 kg research samples will not be collected 	10-20 mL	Streck Cell-Free DNA BCT tubes
Total Blood Volume in 'Time of progression or End of protocol therapy'			10-20 mL	

*Only for patients receiving \geq 5 cycles of therapy only

APPENDIX V: BVD-523FB (ULIXERTINIB) DOSING NOMOGRAM**BVD-523FB (ulixertinib) Dose Assignment: 175 mg/m²/dose PO BID
(Dose Level -1)**

BSA (m ²)	BVD-523FB (ulixertinib) dosing	Total Daily dose (mg/day)	Total Daily pill count	Dose Reduction for Toxicity
0.54-0.72	Off-Study	Off-Study	Off-study	Off-study
0.73-1.07	150 mg PO BID	300	2	Off-Study
1.08-1.58	300 mg PO AM, 150 mg PO PM	450	3	150 mg PO BID
≥1.59	300 mg PO BID	600	4	300 mg PO AM, 150 mg PO PM

**BVD-523FB (ulixertinib) Dose Assignment: 260 mg/m²/dose PO BID
(Dose Level 1)**

BSA (m ²)	BVD-523FB (ulixertinib) dosing	Total Daily dose (mg/day)	Total Daily pill count	Dose Reduction for Toxicity
0.54-0.72	150 mg PO BID	300	2	off study
0.73-1.07	300 mg PO AM, 150 mg PO PM	450	3	150 mg PO BID
1.08-1.29	300 mg PO BID	600	4	300 mg PO AM, 150 mg PO PM
1.3-1.58	450 mg PO AM, 300 mg PO PM	750	5	300 mg PO AM, 150 mg PO PM
≥1.59	450 mg PO BID	900	6	300 mg PO BID

**BVD-523FB (ulixertinib) Dose Assignment: 350 mg/m²/dose PO BID
(Dose Level 2)**

BSA (m ²)	BVD-523FB (ulixertinib) dosing	Total Daily dose (mg/day)	Total Daily pill count	Dose Reduction for Toxicity
0.54-0.72	300 mg PO AM, 150 mg PO PM	450	3	150 mg PO BID
0.73-1.07	300 mg PO BID	600	4	300 mg PO AM, 150 mg PO PM

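### At exactly 3 days of Grade 3 nausea or vomiting, the Section 6.4 tables contradict the DLT definition in Section 5.4.1.1; the definition should govern and the tables should be corrected

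*Combined protocol and SAP*

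**What the plan says.** Three places bear on the point, all in the combined protocol and SAP.

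- **Section 5.4.1.1 (definition).** Attributable non-hematological toxicity of Grade 3 or above is a DLT, with listed exceptions. The exception here is "Grade 3 nausea and vomiting of less < 3 days duration".
- **Section 6.4 (management tables).** The Grade 3 nausea row says to hold the drug and then: "If Grade 3 nausea persists for > 3 days, this will be considered a DLT". The Grade 3 vomiting row repeats the rule: "If Grade 3 vomiting persists for > 3 days, this will be considered a DLT". Both rows then prescribe a one-level reduction and refer to Section 6.2.
- **Section 6.2 (general rule).** Section 6.2.1 applies the hold and the reduced dose to DLTs as Section 5.4.1 defines them, and adds: "Doses reduced for toxicity will not be re-escalated, even if there is minimal or no toxicity with the reduced dose". Section 6.2.3 requires removal from protocol therapy if a DLT comes back at the reduced dose.

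For dose finding, Section 5.1.1 turns on two DLTs in six. The escalation rule begins "If there are fewer than 2 DLTs in the first 6 toxicity-evaluable subjects enrolled at the starting dose", and two or more send the next cohort to Dose Level -1.

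**The concern.** A DLT threshold should read the same in the definition and in the table that a treating physician opens when a child is vomiting. Here the definition counts an episode of exactly 3 days and the table's stated trigger does not reach it.

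Two things depend on the classification.

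- **The child's dose, in any cycle.** A DLT brings a permanent reduction. Appendix V sets it at 25% to 40% of the daily dose. Where no lower dose exists, the child goes off study (BSA 0.54-0.72 m² at Dose Level 1, 0.73-1.07 m² at Dose Level -1). A site that relies on the table might restart at full dose.
- **The cohort decision, in Cycle 1.** One uncounted DLT can leave a cohort at 1 of 6 when it should be 2 of 6.

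**Working it through.** **Step 1. Compare the two rules by duration d, in days.** Section 5.4.1.1: DLT unless d < 3. Section 6.4: DLT if d > 3.

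| d | 5.4.1.1 | 6.4 trigger met |
|---|---|---|
| 2 | no | no |
| 2.5 | no | no |
| 3 | **yes** | **no** |
| 3.5 | yes | yes |
| 4 | yes | yes |

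The only disagreement is at d = 3. That value is plausible if durations are recorded in whole days. This is an inference: Section 13.4.3 says "The duration of the AE is defined as the duration of the highest (most severe) grade of the Adverse Effects" but does not name a unit, and the note to Section 13.4 limits those rules to case report forms.

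**Step 2. Which rule governs.** The 6.4 rows send the reduction to Section 6.2. Section 6.2.1 sends the trigger to Section 5.4.1. The chain ends at the definition, so a 3-day episode is a DLT and requires the reduction.

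**Step 3. What a reduction costs.** Daily doses before and after, from Appendix V:

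- Dose Level 1: 450 to 300 mg (33%), 600 to 450 (25%), 750 to 450 (40%), 900 to 600 (33%).
- Dose Level 2: 450 to 300 (33%), 600 to 450 (25%), 900 to 600 (33%), 1050 to 750 (29%), 1200 to 900 (25%).

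**Step 4. How often the cut-offs would split a cohort decision.** Section 2.3.1 gives adult nausea of any grade as 42%, but the documents give no Grade 3 rate or duration. Assumptions:

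- Grade 3 nausea or vomiting in Cycle 1 in 2% to 10% of patients.
- 10% to 30% of those episodes last exactly 3 days. So q, the per-patient chance of such a case, runs from 0.02 × 0.10 = 0.002 to 0.10 × 0.30 = 0.03.
- Other DLTs occur with probability p = 0.10 to 0.30.

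At least one 3-day case in six patients is 1 − (1 − q)^6, which is 1.2% at q = 0.002 and 16.7% at q = 0.03.

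The decision differs when there is at most one other DLT, but two or more once the 3-day cases are added. With X ~ Bin(6, ·), that probability is P(X ≥ 2 at p + q) − P(X ≥ 2 at p). For p = 0.20 and q = 0.03 it is 0.418 − 0.345 = 0.073.

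| q | p = 0.10 | p = 0.20 | p = 0.30 |
|---|---|---|---|
| 0.002 | 0.4% | 0.5% | 0.4% |
| 0.01 | 2.0% | 2.5% | 2.1% |
| 0.03 | 6.3% | 7.3% | 6.2% |

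Under the rolling-six rules of Section 11.2.2, with complete data at each entry, full enumeration gives 0.3% to 6.5% over the same grid.

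Given one such case in a full cohort of six, the decision differs if exactly one of the other five has another DLT: 5p(1 − p)^4 = 0.328, 0.410 and 0.360 for p = 0.10, 0.20 and 0.30.

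**Step 5. Does the patient still count?** Cycle 1 has 28 × 2 = 56 doses. A hold of exactly 3 days misses 6, leaving 50/56 = 89%, above the 85% required by Section 11.6 for a patient without a DLT. That patient would then be counted as a non-DLT. This holds only while at most 8 doses are missed (48/56 = 85.7%; 47/56 = 83.9%). A longer hold would make a patient classed as non-DLT inevaluable, and that patient would be replaced under Section 11.2.2.

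**The case against.** The best defence is that the plan already answers the question. Section 5.4 is the definition, Section 6.2.1 points to it, and the 6.4 rows point to 6.2. The tables give a sufficient condition for a DLT and never say that a 3-day episode is not one. Read together, the sections require the reduction, and 6.4 is merely incomplete at one value. This stands, and it is why the error lies in 6.4 and not in the definition.

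The second defence is central oversight. Section 5.3 sends suspected DLTs to the Study Chair within 24 hours, and Section 6.0 requires notice of dose modifications. Under Section 14.4.2 the Study Chair enters DLTs in the database and MATCH leadership reviews them weekly. This also stands, and makes a wrong cohort decision unlikely. It does not remove the problem. The 24-hour report depends on the site suspecting a DLT, and a restart at the same dose may not be seen as a modification to notify.

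A reader might infer three stronger points that the documents do not support.

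- **The governing cut-off is undefined, or 6.4 exempts 3-day episodes.** The cross-reference in 6.2.1 argues against both.
- **The two Grade 2 bullets are excluded from DLT because they follow the exclusion list in 5.4.1.1.** Sections 6.3 and 6.4 treat persistent Grade 2 events as DLTs, a Grade 2 event cannot be an exception to a rule for Grade 3 and above, and the placement may be a layout effect of text extraction.
- **The lack of a stated restart dose for shorter Grade 3 episodes is part of the same mistake.** It is a missing detail and creates no contradiction.

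**Conclusion.** The inconsistency is real and narrow. At exactly 3 days, Section 5.4.1.1 makes attributable Grade 3 nausea or vomiting a DLT, while the 6.4 tables set their trigger just above it. The definition should govern, so the tables are wrong at that value.

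The more direct consequence is for the individual child: an unreported DLT, or a restart without the required 25% to 40% reduction or removal. The dose-finding consequence has low probability. The 0.4% to 7.3% range is the chance that the two cut-offs disagree about a cohort. It is not the chance of a wrong decision, which is lower and cannot be estimated from the documents. The range rests entirely on assumed rates and on whole-day counting. The 33% to 41% figure applies only once such a case has occurred. A reader might infer that the selected dose is at serious risk; the oversight arrangements and these figures do not support that. The primary response analysis, its sample size and its decision rule are unaffected.

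**What to change.** In Section 6.4, change the Grade 3 trigger from more than 3 days to 3 days or more (≥ 3 days) in both the nausea and the vomiting table, to match Section 5.4.1.1. In Section 5.4.1.1, correct the doubled comparison so that the exclusion reads simply < 3 days.

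The cost is two table cells and one wording correction, with no new data, visits or patients. Two optional clarifications could go in the same amendment: a restart dose for Grade 3 nausea or vomiting of under 3 days, and separate numbering for the two Grade 2 criteria. Neither is needed to remove the contradiction.
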